#### 2) Blinding

The clinicians and patients will be blinded to the intention of the group divided. Since the patients' and clinicians' subjective motion may affect the outcomes.

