## **Methods:**

### Overview of design:

A randomized, open, blank controlled, single-center clinical trial was conducted to compare the survival benefits of statins in breast cancer patients with dyslipidemia (low and medium risk of ASCVD). The control group used dietary intervention instead of statins. The main endpoint was 5 years DFS. The subjects were breast cancer patients. In this study, 348 patients were randomly divided into two groups according to patients' wishes and written informed consent. The experimental group: control group = 1:1. Subjects were screened and administered continuously until the disease progressed and the toxicity was intolerable. Informed consent was withdrawn or the researcher decided that the drug must be discontinued.

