#### 1) Randomization

We prepare to use SPSS software to do the randomly separation. According to the inclusions and exclusions, once we find the right patient, we will put the name in computer. The computer will randomly tell which group the patient will be in. After explanations to the patients, and receiving the patient agreements, we will sign the informed consent with them.

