### **Data safety & monitoring:**

The members of DSMB are 3 professors in the breast surgery department, 6 attending doctors and 3 residents. DSMB members will meet:

- 1) before the start of the trial to discuss the study protocol,
- 2) at early stage of about 10-20 patients are enrolled. In order to monitor **enrollment** efficacy, **adverse effects** that might have happened, the efficacy of **blinding** strategy, the current **outcome variables** in control and interventional group (only known to DSMB members), **protocol** compliance and quality control issues.
- 3) Subsequent DSMB meetings will be hold regularly (at least every three months) or anytime when there are safety issues, need to stop the program earlier and so on.

If DSMB find that the statins are causing harm, they could discuss whether to end the study early after balancing between ethical responsibility to the participants and the advance of scientific knowledge.

If DSMB find that the statins are much more effective than anticipated, they could stop the study before the primary endpoint.

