## **Ethical considerations:**

In our study, the major ethical issue is the applied population of statins. In order to mitigate this situation, we will:

- 1) Specify the inclusion criteria that specific patients.
- 2) We will monitor patients' liver function and blood lipid levels and adjust the dosage of drugs accordingly.
- 3) Inform the patients with this potential risk comprehensively, have them better understood the potential risk of this study, and write it in the informed consent.
- 4) Use DSMB to monitor any risk related to the intervention.

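### The protocol cites blinding of clinicians and patients as protection for its outcomes, but the trial is open, statin against diet with no placebo, so DFS ascertainment lacks that protection

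*Combined protocol and SAP*

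**What the plan says.** Under Methods, Overview of design, the trial is described as "A randomized, open, blank controlled, single-center clinical trial was conducted", and the comparison is given as "The control group used dietary intervention instead of statins". No placebo, sham or masked supply appears anywhere in the documents.

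The section headed 2) Blinding reads "The clinicians and patients will be blinded to the intention of the group divided", with the reason "Since the patients' and clinicians' subjective motion may affect the outcomes". Data safety & monitoring lists "the efficacy of blinding strategy" among the items the DSMB reviews. It also says that current outcomes by group are known only to DSMB members.

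Three other places bear on who knows the arm:
- **1) Randomization:** "The computer will randomly tell which group the patient will be in", once the patient's name has been entered.
- **Ethical considerations:** "We will monitor patients' liver function and blood lipid levels and adjust the dosage of drugs accordingly".
- **Appendix follow-up form:** the title names both treatments, and there is a field for the statin at baseline and at every later visit.

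**The concern.** The protocol identifies a bias risk, names blinding as the safeguard, and describes a design that cannot supply it. The exposure is mainly in DFS, the primary outcome, because a recorded DFS time depends on when recurrence is looked for and when it is called. Both can differ between arms when the treating clinician and the patient know the treatment. Overall survival, the secondary outcome, is much less exposed.

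The plan offers no substitute. It describes no masked outcome assessor and no independent endpoint review. The appraiser mentioned under 3) Run-in design does the diagnostic evaluation at enrolment, not the assessment of recurrence. A report that repeated the Blinding section would describe the trial as better protected than it is.

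**Working it through.** The point is textual, and the plan gives no figure to reproduce. The check sets the statements side by side under each possible meaning of the Blinding sentence.

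**Reading A: treatment allocation is masked.** This contradicts the Overview of design, which says open. It is also unworkable with a drug in one arm, a diet in the other and no placebo. The patient knows whether she takes a tablet. Staff receive the group from the computer, adjust the drug dose against liver function and lipids, and fill in the statin field at each visit.

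**Reading B: only the hypothesis is masked.** This can coexist with an open trial. The stated reason, however, is to stop subjective views from affecting outcomes. People who know each patient's treatment can still look for, or call, recurrence differently by arm, so this reading does not deliver the protection either. The DSMB item also treats blinding as a working strategy whose success can be checked, and the protocol says nothing about how hiding the hypothesis would be checked.

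Both readings lead to the same result: treatment is known to those whose judgement the section sets out to neutralise.

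**Does the form equalise recurrence surveillance?** It sets the same visits for everyone, with LDL-C, TC, TG, ALT, CK and fatty liver at each. It names no recurrence imaging. The recurrence-time field appears at 6 months and at 1, 1.5, 2, 3, 4 and 5 years. It is missing at 1 and 3 months and at 2.5, 3.5 and 4.5 years. The form therefore sets a common visit calendar but no schedule for assessing recurrence.

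**Illustration only.** Assume no true effect, 157 per arm (Statistical issues, Primary outcomes), common 5-year DFS p, and a shift s in recorded DFS caused by knowing the arm. For a two-sided 5% test of two proportions:

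- standardised shift: δ = s / √(2p(1−p)/157)
- rejection rate: Φ(−1.96 + δ) + Φ(−1.96 − δ)

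For p = 0.80 and s = 0.02: √(0.32/157) = 0.0451, δ = 0.443, and the rate is 0.065 + 0.008 = 7.3%.

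| Assumed DFS | 2-point shift | 3-point shift |
|---|---|---|
| 80% | 7.3% | 10.2% |
| 85% | 7.9% | 11.5% |
| 90% | 9.1% | 14.4% |

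The DFS levels and the shifts are assumptions; the documents support neither. The Abstract names the log-rank test for the survival curves, not a comparison of proportions.

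**The case against.** The strongest defence is that the Blinding sentence is qualified. It says clinicians and patients are blinded to the intention behind the grouping, which need not mean blinded to treatment. A reader might infer that the protocol flatly claims masked allocation; the wording does not establish that.

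A reader might also infer that masking the hypothesis is ruled out because patients receive explanations before consent and because Ethical considerations says "Inform the patients with this potential risk comprehensively". That does not follow. The content of the explanations is not stated, and disclosing risk is not the same as disclosing the DFS hypothesis. The consent pages are not available for checking.

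It is also fair to say that an open design is legitimate for drug against diet, that it is declared, and that no sample-size or analysis step depends on blinding. The Abstract assigns randomization to a group independent of the research team, but that protects allocation, not the later assessment of recurrence.

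Finally, the false-positive figures describe open-label bias in general. That bias would be the same whether or not the Blinding section were reworded.

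All of this stands, and it limits the point. It does not remove it: under the milder reading the stated purpose is still unmet, and nothing else in the plan meets it for DFS.

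**Conclusion.** The point holds in limited form. Overview of design, Blinding, and Data safety & monitoring need to be reconciled, because the protection claimed against subjective influence on DFS is absent whichever way the Blinding sentence is read. This conclusion rests on the text alone and needs no numerical assumption.

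The documents do not support going further, to a finding that DFS will be biased or that the error rate is inflated by a known amount. The 7-9% range for a 2-point shift shows only what such a shift would do if it occurred. Nor is the choice of an open design itself at fault. The correction should be made because it is cheap and concerns how the primary outcome is ascertained.

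**What to change.** 1. State in Overview of design and in Blinding that the trial is open-label, and remove the claim that clinicians and patients are blinded.
2. Date recurrence from the routine imaging or pathology report, with the arm left off the request.
3. State that one recurrence-assessment schedule applies in both arms. The current form does not set one. This is needed alongside item 2, because leaving the arm off a request does not stop a clinician who knows the arm from ordering tests earlier in one group. The intervals are for the sponsor to set.
4. Have the analyst work with coded arms.
5. Redefine the DSMB item as monitoring of this masking, and keep outcomes by group known only to the DSMB, as the section already provides.

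None of this needs extra staff. The cost is a protocol rewording and minor procedural work on request forms and data coding. The downside is that the trial can no longer be described as blinded.

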#### 3) Run-in design

We would like to recruit patients from the breast surgery department. Clinic doctors in this department will help us to find appropriate patients. Then appraiser will do the diagnostic evaluation. If patients meet the included standard, we will ask them to sign informed consent and the registration form (questionnaire). Meanwhile we will make a calendar for their treatment and supervision.

#### 4) Stratified blocked randomization

In clinical practice, different molecular subtypes do relate to different prognosis and treatment. So we would like to stratify blocked randomization according to molecular subtype. Previous study [12] show that the proportion of luminal A, luminal B, Her-2 positive and triple-negative are 32.73%, 47.01%, 5.71%, 14.55%. And we will do subgroup analysis.

#### **Statistical issues:**

### Primary outcomes:

The research question is whether statins can benefit breast cancer patients with dyslipidemia (low and medium risk of ASCVD). The main endpoint was DFS. A review of the literature suggests that simvastatin reduced the recurrence rate of breast cancer by 10%. The investigator would like to be able to detect a difference of 10% or more in DFS change between the two groups. How many patients are required in each group at  $\alpha$  (two-sided) = 0.05;  $\beta$  = 0.10, power = 0.90.

1. Null Hypothesis: For breast cancer patients with dyslipidemia (low and medium risk of ASCVD) under endocrine therapy, whether statin used is the same in DFS.
2. Alternative Hypothesis (two-sided): For breast cancer patients with dyslipidemia (low and medium risk of ASCVD) under endocrine therapy, whether statin used is different in DFS.
3. Effect size=0.1(10%\*2)
4. Standard deviation of CTC=1
5. Standardized effect size=effect size/standard deviation=0.1/1=0.1
6.  $\alpha$  (two-sided) = 0.05;  $\beta$  = 0.10, power = 0.9
7. Based on Appendix 6A from the text book, the estimated sample size is 157 in each group.
8. Ultimate sample size =  $2*157/0.9= 348$

Looking across from a standardized effect size of 0.10 in the leftmost column in Table 6A and down from  $\alpha$  (two-side) =0.05 and  $\beta$  = 0.10 is the required sample size of 157patients in statins group and control group. With 10% dropout the final sample size is 348[14].

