**Abstract:**

This is a randomized clinical trial from March 28st 2019 to March 28st 2024. The purpose of this study is to evaluate the survival benefits of statins in breast cancer patients with abnormal lipid metabolism. Consecutive samples will be enrolled based on inclusion and exclusion criteria. They will be grouped randomly into intervention group or control group after informed consent. A third group independent from research team will be in charge of randomization. In this study, 348 patients were randomly divided into two groups according to patients' wishes and written informed consent. The experimental group: control group = 1:1. Patients in both groups will undergo breast cancer treatment. The experimental group used statins, while the control group used dietary intervention instead of statins. The main endpoint was 5 years DFS. The subjects were breast cancer patients. For statistical analysis, t-test will be used between two different groups. Estimated sample size will be calculated using t-test. Log rank test was used with survival curve based on Kaplan Merier method and 95% confidence interval of median survival time. Data and Safety Monitoring Board will periodically review, evaluate and give recommendations to this study in various aspects.

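### The 157 patients per arm do not follow from the stated inputs, and the 90% power is unsupported for DFS

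*Combined protocol and SAP*

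**What the plan says.** Under Statistical issues, Primary outcomes, the target is set as follows: "The investigator would like to be able to detect a difference of 10% or more in DFS change between the two groups". Step 3 gives an effect size of 0.1, annotated as 10% × 2. Step 4 gives "Standard deviation of CTC=1", and step 5 "Standardized effect size=effect size/standard deviation=0.1/1=0.1". With two-sided alpha 0.05 and power 0.90, step 7 reads: "Based on Appendix 6A from the text book, the estimated sample size is 157 in each group". Step 8 computes 2 × 157/0.9 and reports 348. The closing paragraph repeats the derivation, starting "Looking across from a standardized effect size of 0.10 in the leftmost column in Table 6A", and arrives at 157 again.

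The Abstract says "Estimated sample size will be calculated using t-test". It names a t-test between groups and also a log-rank analysis: "Log rank test was used with survival curve based on Kaplan Merier method and 95% confidence interval of median survival time". The main endpoint is 5-year DFS in the Abstract and the Overview of design, and a DFS rate under Measurements.

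**The concern.** A standardized effect of 0.10 is small, and 157 per group is far too few to detect it with 90% power. The same inputs and result appear twice, so one mistyped step does not explain the gap.

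The inputs also seem to belong to another study. CTC is not defined, is not an outcome under Measurements, and is not on the case report form in the Appendix. A difference in means divided by a standard deviation is not the effect measure for either a log-rank test or a comparison of 5-year DFS rates.

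This is the plan's only justification for 348 patients and for its power on the primary endpoint. If it fails, a non-significant DFS result could be read as coming from a trial with 90% power when nothing in the plan supports that figure.

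**Working it through.** **1. The plan's own figure.** Inputs from Primary outcomes, steps 3 to 6: d = 0.1, SD = 1, two-sided alpha 0.05 (z = 1.960), power 0.90 (z = 1.282).

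n per group = 2 × (1.960 + 1.282)² / d²

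- d = 0.1: 2 × 10.507 / 0.01 = 2,101.5. The exact t-test gives 2,102.4, so 2,103 per group, about 13 times 157. Power at 157 per group is 14%.
- d = 0.2 (the 10% × 2 note): 2 × 10.507 / 0.04 = 525.4. The exact t-test gives 526.3, so 527 per group. Power at 157 is 42%.
- 157 per group gives 90% power only at d of about 0.367, a value that appears nowhere in the documents.
- Variants at d = 0.1 (normal approximation): one-sided 90%, 1,713; two-sided 80%, 1,570; one-sided 80%, 1,237; one-sample 90%, 1,051. None is 157.

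**2. Dropout step.** 2 × 157/0.9 = 348.9, reported as 348. The method is sound; rounding up would give 349.

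**3. DFS scale, absolute 10-point gain.** The documents give no control rate, so the rates below are assumptions. DFS is taken as exponential, with 157 per arm and every patient followed for 5 years.

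- HR = ln(S₁)/ln(S₀), where S₀ and S₁ are 5-year DFS on control and statin
- Events needed = 4 × (1.960 + 1.282)² / (ln HR)² (Schoenfeld)
- Expected events D = 157 × [(1 − S₀) + (1 − S₁)]
- Log-rank power = Φ(√D × |ln HR|/2 − 1.960)
- Two-proportion power = Φ{[0.10√157 − 1.960√(2p̄(1 − p̄))] / √[S₀(1 − S₀) + S₁(1 − S₁)]}, where p̄ is the mean of S₀ and S₁

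Worked for 80 vs 90%:

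- HR = 0.1054/0.2231 = 0.472, so |ln HR| = 0.750.
- Events needed = 42.03/0.563 = 74.6; expected = 157 × 0.30 = 47.1.
- Log-rank power = Φ(6.863 × 0.375 − 1.960) = 73%.
- Two-proportion power = Φ[(1.253 − 0.990)/0.500] = 70%.

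| 5-year DFS | HR | Events expected / needed | Log-rank, Schoenfeld | Log-rank, simulated | Two proportions |
|---|---|---|---|---|---|
| 70 vs 80% | 0.626 | 78.5 / 191.1 | 55% | 54% | 53% |
| 75 vs 85% | 0.565 | 62.8 / 128.9 | 62% | 61% | 60% |
| 80 vs 90% | 0.472 | 47.1 / 74.6 | 73% | 72% | 70% |
| 85 vs 95% | 0.316 | 31.4 / 31.6 | 90% | 86% | 84% |

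The simulations used 6,000 runs per row. The Schoenfeld formula is generous at HR 0.316, so 86% is the better figure for the last row. At 87 vs 97%, two-proportion power is 91%.

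**4. Shorter follow-up.** The Abstract says: "This is a randomized clinical trial from March 28st 2019 to March 28st 2024". If analysis falls at the end of that five-year window and accrual is uniform over 1, 2 or 3 years (assumed), Schoenfeld power is 69/64/59% for 80 vs 90% (43/38/34 events) and 87/83/78% for 85 vs 95% (28/25/22 events). Simulation gives 67/61/54% and 82/78/72%.

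**5. Relative reading.** The plan's source for the effect is a 10% reduction in recurrence, not identified as absolute or relative. If it is relative, with an assumed control recurrence of 10% to 40%, two-proportion power at 157 per arm is about 5% to 11%.

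**The case against.** **High control DFS.** The strongest defence is that the conclusion could be right even though the derivation is wrong. With control 5-year DFS of about 87% or higher and an absolute 10-point gain, 157 per arm can give 90% power. This stands, and it is why the claim is called unsupported rather than false on the DFS scale. The plan states no such rate, and the favourable case also needs an absolute reading of the 10% and full follow-up.

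**Another source for 157.** An 80 vs 90% comparison at one-sided 0.05 and 80% power gives exactly 157, and the two-sided 80% answer at d = 0.1 is 1,570, ten times larger. Neither is shown to be the source, and both contradict the stated 90% power. The textbook table was not available, but the t-test formula settles the arithmetic without it.

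**Follow-up.** The Abstract gives trial dates, not a censoring rule, and the case report form schedules a 5-year visit for each patient. Follow-up beyond March 2024 may be intended, so the reduced-follow-up figures are conditional. The two places still need reconciling.

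**Consequence.** The error introduces no bias and does not inflate the type I error. That is correct and limits the harm to the power claim and the basis for 348.

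**Conclusion.** The concern holds. On the stated inputs the 90% power is wrong: 2,103 per group would be needed, and 157 gives 14% (42% if the effect is 0.2). This part rests only on the protocol's own numbers.

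On the DFS scale the 90% cannot be verified. With an absolute 10-point gain, exponential DFS, full 5-year follow-up and assumed control rates of 70% to 85%, power is about 53% to 86% across the two-proportion and simulated log-rank results. It would be lower with administrative censoring inside the five-year window, and far lower if the 10% is relative. The t-test figures show that the derivation failed; they are not the trial's DFS power. The correction is needed because no other justification of the sample size exists.

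**What to change.** Replace steps 3 to 8 and the closing paragraph with a calculation matched to the primary DFS analysis: events-based if the log-rank test is primary, two proportions if the 5-year DFS rate is primary. It should state:

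- the assumed control 5-year DFS and its source;
- whether the 10% is absolute or relative;
- the implied hazard ratio (for example 0.47 for 80 vs 90%, 0.32 for 85 vs 95%);
- the accrual period, follow-up per patient and expected events.

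Reconcile follow-up with the March 2019 to March 2024 window before quoting a power. The full-follow-up figures above are best cases and should not be copied into the protocol. If the hazard ratio is as extreme as 0.32, check the power by simulation.

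Delete the CTC standard deviation and correct the Abstract's sentence on sizing by t-test. Replace the 0.90 with the power that the evaluable patients give under the stated assumptions (0.9 × 348 = 313.2, so about 313).

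The cost is protocol and SAP wording. The stated power would fall below 90% under most of the control rates shown. The correction is to restate the power; it does not call for more enrolment.

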### **Data safety & monitoring:**

The members of DSMB are 3 professors in the breast surgery department, 6 attending doctors and 3 residents. DSMB members will meet:

- 1) before the start of the trial to discuss the study protocol,
- 2) at early stage of about 10-20 patients are enrolled. In order to monitor **enrollment** efficacy, **adverse effects** that might have happened, the efficacy of **blinding** strategy, the current **outcome variables** in control and interventional group (only known to DSMB members), **protocol** compliance and quality control issues.
- 3) Subsequent DSMB meetings will be hold regularly (at least every three months) or anytime when there are safety issues, need to stop the program earlier and so on.

If DSMB find that the statins are causing harm, they could discuss whether to end the study early after balancing between ethical responsibility to the participants and the advance of scientific knowledge.

If DSMB find that the statins are much more effective than anticipated, they could stop the study before the primary endpoint.

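### At least 3 of the 12 monitoring board members belong to the recruiting department, and no rule keeps members who see outcomes by arm from recruiting, treating or assessing trial patients

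*Combined protocol and SAP*

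**What the plan says.** **Board membership.** Data safety & monitoring states: "The members of DSMB are 3 professors in the breast surgery department, 6 attending doctors and 3 residents". It names no statistician and no member from outside the hospital.

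**Recruitment.** 3) Run-in design says "We would like to recruit patients from the breast surgery department" and "Clinic doctors in this department will help us to find appropriate patients".

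**What the board sees, and when.** After a meeting before the trial starts, the next is "at early stage of about 10-20 patients are enrolled". Its agenda includes the current outcome variables "in control and interventional group (only known to DSMB members". Then: "Subsequent DSMB meetings will be hold regularly (at least every three months", or sooner if a safety issue arises. No agenda is given for these later meetings.

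**What the board may do.** It may consider ending the trial for harm, and may stop before the primary endpoint if statins do much better than planned. No boundary is stated.

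**Design.** Overview of design: "A randomized, open, blank controlled, single-center clinical trial was conducted". The section 2) Blinding says instead: "The clinicians and patients will be blinded to the intention of the group divided".

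**Independence.** The Abstract says that a group independent of the research team handles randomisation. Nothing similar is said of the board.

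**The concern.** The plan means interim results by arm to stay confidential, and does this by limiting them to board members. That works only if board members are not also the people running the trial. Here at least three of them sit in the department that supplies the patients, and no rule separates the two roles.

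A doctor who knows the interim trend and also has a trial role could influence the result in three ways:

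- **Enrolment.** Under 1) Randomization, the computer gives the group before the patient is counselled and consent is signed. A recruiter who knew the trend would also know the arm while consent was still open.
- **Endpoint.** The plan does not define a DFS event or provide a blinded DFS assessor. The Appendix form records recurrence time as a free entry. When recurrence is looked for and declared is therefore open to judgement.
- **Stopping.** The same board may end the trial for benefit.

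What is at stake is the credibility of the DFS comparison and of any early stop.

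**Working it through.** The plan gives no figure for this point, so the check is a count followed by a comparison of sections.

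**1. Board.** 3 + 6 + 3 = 12 members. The breast surgery department is attached in words to the 3 professors only, so the overlap is at least 3 of 12 (25%). For the other 12 - 3 = 9, no department is given.

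**2. Meetings.** The Abstract gives a five-year period, March 2019 to March 2024. At least one meeting every three months gives 5 x 4 = 20, so about 20 meetings. This is not a count of by-arm analyses.

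**3. First by-arm review.** It falls at about 10-20 of 348 patients: 10/348 = 2.9% to 20/348 = 5.7% of enrolment. Between 348 - 20 = 328 and 348 - 10 = 338 patients are still to be enrolled. At 1:1 allocation there are about 5-10 patients per arm, so this review alone says little about efficacy. The exposure that matters is at later meetings.

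**4. Is by-arm review implied later?** The agenda is silent. But the board may stop if statins do much better than planned, and that cannot be decided without comparing the arms. Further by-arm review is therefore implied, at an unknown number of meetings.

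**5. Do the roles overlap?**

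| Role | Who, according to the plan | Separated from the board? |
|---|---|---|
| Finds patients | Clinic doctors of the breast surgery department | No rule stated |
| Treats patients | Not named; single centre | No rule stated |
| Assesses DFS | Not named | No rule stated |
| Sees outcomes by arm | Board: 3 professors of that department and 9 others | - |

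The plan does not say that a board member fills any of the first three roles. It also does not exclude it.

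**6. Does blinding close the gap?** Overview of design calls the trial open; 2) Blinding says clinicians and patients do not know the intention of the grouping. The two conflict and must be reconciled. Even read generously, the blinding sentence does not cover a clinician on the board who is shown outcomes by arm.

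**7. Can the bias be sized?** No. The documents give no DFS rate, no test at the interim reviews, and no basis for how far recorded DFS might shift. Any error rate would be set by the assumed shift.

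**The case against.** The strongest reply is that the text establishes less than it suggests, and several inferences a reader might draw are not supported.

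- **That the whole board comes from breast surgery.** This is a natural reading, but the department is tied only to the professors. At least 3 of 12 is what the text supports.
- **That there are about 20 looks at the data by arm.** By-arm outcomes are listed only for the meeting at 10-20 patients. About 20 is the number of meetings.
- **That board members recruit or treat trial patients.** No section says so. The clinic doctors who find patients are not said to sit on the board.
- **That confidentiality is absent.** A restriction to board members is written down. It exists; what it lacks is separation of those members from the conduct of the trial.
- **That the false-positive rate rises by a known amount.** This would need an assumed shift in DFS, and the number of meetings would not supply one.

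Two further points are fair. In an open trial clinicians may already know each patient's arm, so knowledge of the aggregate trend adds to an existing risk by an amount that cannot be isolated. And disclosing the group before consent is a problem whoever sits on the board.

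These limits stand and set the wording. They do not remove the point. Three members from the recruiting department, shown outcomes by arm and free to hold any trial role, are enough to leave the route open if the plan is followed as written.

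**Conclusion.** The point holds as a gap in the design and should be corrected. At least a quarter of the board belongs to the department that recruits. The board sees outcomes by arm early, meets at least quarterly and may stop for benefit, and no rule separates its members from recruitment, treatment or DFS assessment. In a single-centre trial described as open, restricting by-arm results to such a board is not adequate protection.

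This rests on two inferences: that the power to stop for benefit means the arms are compared after the first review, and that silence about dual roles leaves them permitted. Both are reasonable, but neither is stated. The documents show a route to bias, not that bias occurred, and give no basis for its size.

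**What to change.** In Data safety & monitoring, state that:

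1. Anyone who recruits, treats or assesses DFS in trial patients is recused from closed sessions and does not see outcomes by arm.
2. The board is reduced to members who meet that rule.
3. Everyone else sees pooled data only.
4. Closed reports are prepared by someone with no recruiting, treating or assessing role.

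The independent randomisation group named in the Abstract could prepare these reports, but only after a conflict is settled. The sampling and recruitment section and 1) Randomization read as if the study team runs the allocation itself in SPSS. Overview of design and 2) Blinding should be reconciled at the same time.

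**Cost.** The board becomes smaller, which a board of 12 can bear if some members have no trial role. If none qualifies, seats must be swapped to existing hospital staff outside the trial. Sample size, endpoint and treatment are unaffected.
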